10.4. Analysis Populations

All subjects that are operated on by the study device are considered study participants. The following study populations and analysis sets will be defined:

- **Safety Population:** This population will include all subjects that received the study device and will be used for analysis of demographics, disposition data and safety.
- **Modified Intention to Treat Population (mITT):** Following the intention to treat principle, this population Full Analysis Set (FAS): This will include all subjects that received the study device and attended at least one post-baseline assessment. This population will be used for the primary analysis of all efficacy endpoints.
- **Per Protocol Population (PP):** This population will include all subjects that received the study device, meet the inclusion/exclusion criteria, attend all follow-up assessments within the specified window, and have no significant protocol deviations. Subjects that are required to be withdrawn from the study under the protocol (e.g. due to revision) will be included regardless of attendance of follow-up visits unless they are deemed to have significant protocol deviations or failed to meet the inclusion/exclusion criteria. This population will be used as secondary analysis of all efficacy endpoints.

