10.5. Analysis of Primary Endpoint

The primary endpoint of the study is the proportion of subjects achieving post-operative mechanical alignment, defined as $\pm 3^\circ$ from target, assessed at the 1 month study visit, and after undergoing a Navio assisted TKA.

The proportion defined above will be presented along with the associated two-sided 95% confidence interval, to be calculated using exact binomial methods.

Superiority of the proportion of subjects achieving post-operative mechanical alignment, after undergoing a Navio assisted TKA against those in the reference literature (Parratte et al.)⁷ will be achieved if the lower limit of the two-sided 95% confidence interval is greater than 73.4%.

Mechanical alignment will also be summarized using summary statistics.

10.6. Analysis of Secondary Endpoints:

Implant survival rate will be assessed for a final analysis using the number and proportion of subjects who had no implant revisions by the 2-year time point, the associated 95% confidence intervals will be calculated using exact binomial methods. Time to occurrence of revisions will also be analyzed using Kaplan-Meier survival analysis.

KSS, EQ-5D-5L, and FJS scores will be analyzed separately at the end of study using Repeated Measures ANOVA models, prognostic and baseline factors will be adjusted for.

Length of hospital stay, operative time (both skin to skin time and anesthetic time), and radiographic assessments will be assessed using summary statistics. Trends in operative time measures for individual investigators over the course of the study will be assessed.

10.7. Analysis of Safety Endpoints:

The safety endpoints for this study are the number of occurrences and the frequency of subjects reporting: adverse events (AE), serious adverse events (SAE), adverse device effects (ADE), serious adverse device effects (SADE), unanticipated serious adverse device effects (USADE) and device deficiencies (DevD).

In addition, for each event, the following will be summarised: seriousness, the relationship to the investigational device (Navio), relationship to implant, relationship to study procedure, outcome and either the duration of the resolved events or the duration of the events at study completion.

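### For implant survival, the per-protocol attendance rule binds unrevised subjects but is waived for revised ones, so the per-protocol estimate is biased downward

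*Combined protocol and SAP*

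**What the plan says.** Section 10.4 of the protocol requires a PP subject to have received the device, to be eligible, and to "attend all follow-up assessments within the specified window, and have no significant protocol deviations". Table 1 in section 7.1 sets four such visits: 30±7, 182±30, 365±60 and 730±60 days.

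Section 10.4 then makes an exception for subjects whose withdrawal the protocol requires: "e.g. due to revision) will be included regardless of attendance of follow-up visits". That exception has a limit, which repeats two of the general entry criteria: "unless they are deemed to have significant protocol deviations or failed to meet the inclusion/exclusion criteria". Section 8.3 ends participation after revision of any component, so revision always brings the exception into play. Loss to follow-up is listed in section 8.3 only as a reason for which the investigator may withdraw a subject, and it gets no waiver.

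On use of the PP set, section 10.4 says: "This population will be used as secondary analysis of all efficacy endpoints". Of the mITT set it says: "This population will be used for the primary analysis of all efficacy endpoints".

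Implant survival is a secondary endpoint in section 3.2 and is absent from the safety endpoints in section 3.3. Section 10.6 estimates it as "the number and proportion of subjects who had no implant revisions by the 2-year time point", with an exact binomial 95% interval, and adds a Kaplan-Meier analysis of time to revision.

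**The concern.** For implant survival, the event that triggers the waiver is the event being counted. A subject revised on day 300 who had missed the 6-month visit stays in the set, unless a significant deviation is declared. A subject seen with an intact implant on day 791, one day past the 2-year window, is a proven two-year survivor and is removed. So is an unrevised subject whose 1-month visit fell on day 38.

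Kaplan-Meier does not repair this. Censoring would keep the time at risk up to last contact, but the rule deletes the subject and all of that time.

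A PP survival figure below the mITT figure would naturally be read as sensitivity to protocol adherence. Some or all of the gap could come from the membership rule alone.

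**Working it through.** The plan states no survival rate, revision rate or PP size, so it has no figure of its own to reproduce. The check is algebraic, with illustrations.

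**Inputs from the documents:** N = 120 (section 10.1); four visits with windows (section 7.1); attendance waived after revision (section 10.4).

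**Assumptions:** R revisions by 2 years; all subjects otherwise eligible and free of significant deviations; excluded unrevised subjects are true survivors. The only attrition figure in the plan is about 5% at 1 month (section 10.1).

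**Formula.** Let S be true survival, f the share of unrevised subjects who meet the attendance rule, and q the share of revised subjects who stay in the set. Then

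PP survival = S·f / [S·f + (1 − S)·q].

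This is below S whenever q > f. The waiver sets q = 1 as far as attendance is concerned, so the estimate is too low for any f < 1 with R ≥ 1. In counts, the PP revision rate is R / [R + (120 − R)·f]. For small R the rate is inflated by roughly 1/f.

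**Main illustration.** R = 3, so the full set gives 117/120 = 97.5%. In-window attendance v per visit is independent across visits, so f = v⁴.

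| v | f | Unrevised kept, 117f | PP revision rate | PP survival | Shift (points) |
|---|---|---|---|---|---|
| 0.95 | 0.8145 | 95.30 | 3/98.30 = 3.05% | 96.9% | −0.6 |
| 0.90 | 0.6561 | 76.76 | 3/79.76 = 3.76% | 96.2% | −1.3 |
| 0.85 | 0.5220 | 61.07 | 3/64.07 = 4.68% | 95.3% | −2.2 |

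**Correlated attendance.** If the same subjects miss visits repeatedly, f rises from v⁴ towards v. At v = 0.85 with full correlation, f = 0.85 and the PP revision rate is 3/(3 + 99.45) = 2.93%, against 4.68% under independence.

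**Other revision counts, whole subjects.**
- R = 1, f = 0.50: 60/61 = 98.4% against 119/120 = 99.2%, a shift of −0.8 points.
- R = 6, f = 0.80: 91/97 = 93.8% against 114/120 = 95.0%, −1.2 points.
- R = 6, f = 0.50: 57/63 = 90.5% against 95.0%, −4.5 points.

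**Precision.** Exact 95% intervals for R = 3 are 92.9% to 99.5% for 117/120, 91.2% to 99.4% for 94/97 (f = 0.80) and 88.5% to 99.1% for 70/73 (f = 0.60).

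**What removes the bias.** With q = f = 0.80 and R = 3, survival is 93.6/(93.6 + 2.4) = 97.5%, the full-set value. With q = 1 it is 93.6/96.6 = 96.9%.

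**What does not.** If the waiver were simply deleted, a subject revised before the 2-year visit could not attend all four visits, so nearly all revised subjects would leave the set. With f = 0.80 the result would approach 94/94 = 100% (95% interval 96.2% to 100%).

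**The case against.** The strongest reply is that the waiver is sensible. Without it, PP survival would be pushed towards 100%, a device-favouring error that the sponsor evidently meant to avoid. That stands. A reader might infer that the waiver is itself the mistake and should be struck out, but section 8.3 makes later attendance impossible after revision. The bias comes from the all-visits-in-window condition combined with a waiver for one outcome group only.

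A reader might also infer that every revised subject is kept. Section 10.4 still excludes revised subjects who are ineligible or have significant deviations. Section 13 counts out-of-window visits as deviations, so poor attendance before revision could exclude someone if judged significant. These criteria also apply to unrevised subjects, so the asymmetry on attendance remains. The waiver also covers other required withdrawals, such as the study being stopped; revision is its stated example.

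The protocol never lists which endpoints are efficacy endpoints. Section 2.2 speaks of safety, performance and health economic evidence, and section 9.1 documents revisions under safety reporting. Treating survival as efficacy is therefore a reading. It is the natural one, because sections 3.2 and 10.6 place survival with the secondary endpoints. If the sponsor means otherwise, the plan should say so.

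On size, relative inflation of a small revision rate can sound dramatic. In points of survival the main example moves by 0.6 to 2.2, and the intervals overlap almost entirely at f = 0.80. The documents do not support a claim that PP survival will fall well below mITT survival.

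Nor do they support a claim that the error must always run against the device. Some excluded subjects will have unknown status, and unrecorded revisions among those lost to follow-up could offset the downward shift.

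**Conclusion.** The point holds. As written, PP membership for implant survival depends on the outcome, and both PP estimates are biased downward when at least one revision occurs and some otherwise eligible unrevised subjects fail the attendance rule. The direction follows from the text, subject to two conditions: survival is analysed as an efficacy endpoint, and unrecorded revisions among subjects lost to follow-up do not offset the shift.

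The size cannot be derived from the documents. Under the stated assumptions (3 revisions, independent attendance of 95% to 85% per visit) it is about 0.6 to 2.2 percentage points, and smaller if attendance is correlated within subjects.

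The consequence is limited. The mITT analysis is primary and entry to it does not turn on revision. Survival has no hypothesis test or success threshold. What is at risk is a supportive figure and the interpretation of its gap from the mITT figure.

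**What to change.** Amend section 10.4, and carry the change into the SAP, for implant survival only:

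- The visit-attendance and visit-window condition applies to no subject, revised or unrevised. The eligibility and significant-deviation criteria apply equally to both. The waiver is then redundant for this endpoint; it must not be deleted unless the attendance condition goes too.
- Kaplan-Meier: censor unrevised subjects at last contact with known implant status.
- Exact binomial proportion: the denominator is subjects revised by 2 years plus those whose implant status is known at 2 years, in or out of window. Censoring cannot define this denominator, so it has to be stated.
- Treat Kaplan-Meier as the main PP survival estimate, because the binomial denominator still drops unrevised subjects lost before 2 years.

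A simpler alternative is not to report implant survival in the PP set. Either way, state explicitly whether implant survival is an efficacy endpoint.

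The cost is a few sentences of text, with no new data and no additional subjects.

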10.5. Analysis of Primary Endpoint

The primary endpoint of the study is the proportion of subjects achieving post-operative mechanical alignment, defined as $\pm 3^\circ$ from target, assessed at the 1 month study visit, and after undergoing a Navio assisted TKA.

The proportion defined above will be presented along with the associated two-sided 95% confidence interval, to be calculated using exact binomial methods.

Superiority of the proportion of subjects achieving post-operative mechanical alignment, after undergoing a Navio assisted TKA against those in the reference literature (Parratte et al.)⁷ will be achieved if the lower limit of the two-sided 95% confidence interval is greater than 73.4%.

Mechanical alignment will also be summarized using summary statistics.

10.6. Analysis of Secondary Endpoints:

Implant survival rate will be assessed for a final analysis using the number and proportion of subjects who had no implant revisions by the 2-year time point, the associated 95% confidence intervals will be calculated using exact binomial methods. Time to occurrence of revisions will also be analyzed using Kaplan-Meier survival analysis.

KSS, EQ-5D-5L, and FJS scores will be analyzed separately at the end of study using Repeated Measures ANOVA models, prognostic and baseline factors will be adjusted for.

Length of hospital stay, operative time (both skin to skin time and anesthetic time), and radiographic assessments will be assessed using summary statistics. Trends in operative time measures for individual investigators over the course of the study will be assessed.

10.7. Analysis of Safety Endpoints:

The safety endpoints for this study are the number of occurrences and the frequency of subjects reporting: adverse events (AE), serious adverse events (SAE), adverse device effects (ADE), serious adverse device effects (SADE), unanticipated serious adverse device effects (USADE) and device deficiencies (DevD).

In addition, for each event, the following will be summarised: seriousness, the relationship to the investigational device (Navio), relationship to implant, relationship to study procedure, outcome and either the duration of the resolved events or the duration of the events at study completion.

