11. ETHICAL CONSIDERATIONS	20
11.1. Ethical Approval	20
11.2. Protocol Amendments	20
11.3. Informed Consent	20
11.4. Risk – Benefit Analysis	20
A. Study Related Risks	20
B. Study Related Benefits	21
12. MONITORING PROCEDURES	21
12.1. Source Documentation	21
12.2. Direct Access	21
12.3. Site Qualification Visit	21
12.4. Site Initiation Visit	21
12.5. Interim Monitoring Visits	22
12.6. Closeout Visit	22
12.7. Sponsor Audits and Regulatory Inspection	22
12.8. Data Handling and Record Keeping Requirements	22

12.9. Data Recording and Record Retention	22
13. DEVIATIONS FROM PROTOCOL.....	23
13.1. Protocol Deviation Reporting Requirements	23
14. Publication policy.....	23
BIBLIOGRAPHY	24
Appendix 1	
JOURNEY II BCS and CR Component Part Numbers.....	28

ABBREVIATIONS & DEFINITIONS

AE	Adverse Event
ADE	Adverse Device Effect
AP	Anteroposterior
CAPA	Corrective and Preventive Action
CRO	Contract Research Organization
CRF	Case Report Form
EC	Ethics Committee
EQ-5D	EuroQuol 5D
FDA	Food and Drug Administration
FU	Follow-Up
GCP	Good Clinical Practice
ICF	Informed Consent Form
ICH	International Conference on Harmonisation of Technical Requirements for Registration of Pharmaceuticals for Human Use
IRB	Institutional Review Board
ITT	Intention to Treat Population
KSS	Knee Society Score
PI	Principal Investigator
PP	Per-protocol Population
QoL	Quality of life
SAE	Serious Adverse Event
SADE	Serious Adverse Device Effect
TKA	Total Knee Arthroplasty
USADE	Unanticipated Serious Adverse Device Effect

Protocol Synopsis:

Title of Study:	Clinical, Radiographic, and Patient-reported Outcomes associated with the use of the Navio [°] Robotic-assisted Surgical System in Total Knee Arthroplasty
Study Type:	Evidence Generation
Study Device:	Navio [°] Robotic-assisted Surgical System
Study Purpose:	To demonstrate superior accuracy with the Navio [°] Robotic-assisted Surgical System in achieving desired post-operative mechanical alignment, compared to TKA procedures using standard instruments, as well as to document clinical and patient-reported outcomes in subjects receiving TKA with the Navio [°] system.
Study Design:	Multicenter, prospective single-arm cohort study with historical control.
Primary Endpoint:	Post-operative Mechanical Alignment (percentage of subjects achieving target alignment, defined as $\pm 3^\circ$ from target) at one month post-operative.

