2. STUDY OBJECTIVES

2.1. Primary Objective

The primary objective of this study is to demonstrate the superiority of the use of the Navio[°] Robotic-assisted Surgical System in the implantation of the JOURNEY[®] II BCS or CR Systems in achieving post-operative mechanical alignment within $\pm 3^\circ$ of target, as compared to TKA procedures using standard instruments.

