10. STATISTICAL PROCEDURES

10.1. Sample size calculation

Parratte et al.⁷ looked at the effects of postoperative mechanical axis alignment on the survival of TKAs. They found that of the 398 TKAs reviewed in the paper there were 292 (73.4%) which post-operatively were defined as mechanically aligned (with a mechanical axis of $0^\circ \pm 3^\circ$).

This study aims to show superiority in the proportion of TKAs post-operatively defined as mechanically aligned against the reference proportion of 73.4% from above.

It is estimated that the proportion of mechanically aligned TKAs using the Navio system will be around 88%. If this assumption holds then the recruitment of 115 subjects would be sufficient to provide 80% power to show that the lower limit of the two-sided 95% confidence interval for the proportion of mechanically aligned TKAs is greater than 73.4%, hence proving superiority to the reference literature. It is expected that approximately 5% of subjects will be lost to follow up at the 1 month visit and therefore 120 subjects will be recruited for this study.

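### The success rule in 10.5 tests a rate within ±3° of an unfixed target against 73.4%, a rate 10.1 defines as 0° ± 3°, and no like-for-like analysis is planned

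*Combined protocol and SAP*

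**What the plan says.** **Study knees.** The synopsis gives the primary endpoint as "percentage of subjects achieving target alignment, defined as $\pm 3^\circ$ from target". Section 2.1 states the objective as superiority "in achieving post-operative mechanical alignment within $\pm 3^\circ$ of target, as compared to TKA procedures using standard instruments". Section 3.1 uses the same definition, and 10.5 repeats it: "defined as $\pm 3^\circ$ from target, assessed at the 1 month study visit". Section 7.3 lists the target alignment among the operative data recorded at surgery. No section gives it a value, a range or a rule.

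**Reference knees.** Section 10.1 takes its benchmark from a published series of 398 knees, of which "292 (73.4%) which post-operatively were defined as mechanically aligned (with a mechanical axis of $0^\circ \pm 3" degrees. It then states the aim as "superiority in the proportion of TKAs post-operatively defined as mechanically aligned against the reference proportion of 73.4"%, and the planning assumption in the same term: "It is estimated that the proportion of mechanically aligned TKAs using the Navio system will be around 88"%.

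**Decision rule.** Under 10.5, superiority over the reference literature is achieved "if the lower limit of the two-sided 95% confidence interval is greater than 73.4"%. The only other alignment analysis there is descriptive: "Mechanical alignment will also be summarized using summary statistics".

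**The concern.** The numerator is measured from a target recorded knee by knee; the benchmark is measured from 0°. The two definitions agree only if every target is 0°, which the documents do not say. Section 10.1 words the aim and the 88% assumption in the term it has just defined by 0° ± 3°, while 10.5 decides on the target-based rate. One success rule is thus attached to two endpoints.

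Two conclusions are affected. The first is that the device gives a higher proportion of mechanically aligned knees than the reference series. If targets differ from 0°, the rule could be met when the study's rate on the reference definition is no higher than 73.4%. The second is superior accuracy to target (2.1). The documents do not give the historical targets, so 73.4% may be too low or too high as a rate around target. This is the trial's only superiority test, and the historical figure is its only comparator.

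**Working it through.** **Inputs.** Benchmark 0.734, assumed rate 0.88, 115 evaluable, 5% loss and 120 recruited (10.1); exact two-sided 95% interval with lower limit above 73.4% (10.5). With 5% loss, 120 × 0.95 = 114, so n = 114 and n = 115 are both shown. The distribution of targets is not in the documents; every value for it below is assumed.

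**The plan's own figures.** 292/398 = 73.37%, which agrees with 73.4%. The Clopper–Pearson lower limit for x successes is the 0.025 quantile of Beta(x, n − x + 1):

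- n = 115: x = 93 gives 0.7248, x = 94 gives 0.7345.
- n = 114: x = 93 gives 0.7323, x = 94 gives 0.7421.

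Success therefore needs 94 knees at either n. P(X ≥ 94) is 0.0243 (n = 115) or 0.0158 (n = 114) at a true rate of 0.734, and 0.982 or 0.970 at 0.88. The stated 80% power at 115 is not reproduced: the rule has about 98% power at 88%, and 80% power at a true rate of 84.1% (84.8% at n = 114). That is a separate discrepancy on the conservative side, and nothing below depends on it.

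**Model.** Let T be the target's deviation from 0° and E the error around target, normal with SD σ. Then:

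- rate around target = P(|E| < 3)
- rate on the reference definition = P(|T + E| < 3)

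**False claims with errors centred on target.** Fix the study's rate within 0° ± 3° at exactly 0.734, so that there is no gain on the reference definition. Solving 2Φ(3/s) − 1 = 0.734 gives a total SD of s = 2.697°.

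- Targets varying around 0° with SD τ: σ = √(2.697² − τ²).
- Constant target offset m: σ solves Φ((3 − m)/σ) − Φ((−3 − m)/σ) = 0.734.

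In both cases the rate that 10.5 scores is 2Φ(3/σ) − 1.

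| Study targets | σ | Rate scored by 10.5 | Superiority declared, n = 114 | n = 115 |
|---|---|---|---|---|
| all 0° | 2.697 | 73.4% | 1.6% | 2.4% |
| SD 0.5° | 2.650 | 74.2% | 2.5% | 3.8% |
| offset 0.5° | 2.650 | 74.2% | 2.5% | 3.8% |
| SD 1.0° | 2.505 | 76.9% | 9.5% | 13.0% |
| offset 1.0° | 2.496 | 77.1% | 10.2% | 13.9% |
| SD 1.5° | 2.241 | 81.9% | 50.0% | 57.8% |
| offset 1.5° | 2.186 | 83.0% | 62.1% | 69.5% |

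**The other direction.** Suppose a constant target offset m is cancelled by an opposite systematic error, so that achieved alignment is centred on 0° with SD 2.697°. The rate within 0° ± 3° is still 73.4%, but the scored rate is Φ((3 − m)/2.697) − Φ((−3 − m)/2.697). This is 72.6%, 70.2% or 66.3% for m = 0.5°, 1.0° or 1.5°. The rule then passes in 1.0–1.5%, 0.2–0.3% or at most 0.02% of trials.

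**Power of a like-for-like analysis.** If 88% are within ±3° of target, σ = 3/Φ⁻¹(0.94) = 1.930°. With targets varying around 0°, the rate within 0° ± 3° is 2Φ(3/√(1.930² + τ²)) − 1:

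| Target SD | Rate within 0° ± 3° | Passes 73.4%, n = 115 | n = 114 |
|---|---|---|---|
| 0.5° | 86.8% | 95% | 93% |
| 1.0° | 83.3% | 72% | 65% |
| 1.5° | 78.0% | 20% | 15% |

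**The case against.** The strongest reply has four parts.

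*The effect may be nil.* If every target is 0°, the definitions coincide. This stands. It is why the size cannot be stated and why one sentence in the protocol might settle the study side. The documents do not contain that sentence.

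*The decision rule is coherent in its own terms.* Section 10.5 concludes on alignment as it defines it, in line with 2.1 and 3.1; the term mechanically aligned belongs to the sample size section. This stands in part. Accuracy to target is a reasonable primary endpoint and should remain so. But the comparator is still a rate around 0°, and a 0° ± 3° analysis does not by itself repair the accuracy-to-target comparison, which depends on historical targets the documents do not give.

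*The rate can be recovered later.* Film and target are collected, alignment will be summarized, and 10.2 foresees a separate SAP. But no 0° ± 3° proportion is named, the success rule is already set in 10.5, and a rate first calculated after the results are known would not have pre-specified standing.

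*The bias may be small or favourable.* This also stands. Two stronger readings are tempting and not supported:

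- A reader might infer that scoring against target flatters the device. That holds only if errors are centred on target. With 88% on target and offsets of 0.5°, 1.0° or 1.5° cancelled by opposite systematic error, the rate within 0° ± 3° would be 89.3%, 93.1% or 98.1%, above 88%.
- With 88% on target and target SD 0.5°, 1.0° or 1.5°, the 10.5 rule passes while the same knees fail a 0° ± 3° test in about 4%, 27% or 78% of trials (n = 115). A reader might take these as false claims. They are not: the true rates within 0° ± 3° are 86.8%, 83.3% and 78.0%, all above 73.4%, so these are failures to confirm something true. At 88% on target with centred errors, the true rate falls to 73.4% only at a target SD of 1.88° or an offset of 1.75°.

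**Conclusion.** The definition mismatch is in the text, and confidence in it is high. The study rate is scored around a target that is not fixed at 0°, the benchmark is scored around 0°, and no planned analysis puts both on one scale.

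The consequence is conditional. With all targets at 0° there is none, and the rule keeps its error rate of 1.6–2.4%. Under the assumed normal model with centred errors, the chance of declaring superiority without any gain on the reference definition is 2.5–3.8%, 9–14% or 50–69% for target differences of 0.5°, 1.0° or 1.5°. With cancelling systematic errors it falls below the nominal 2.5%. These are illustrations, not estimates. The documents do not support saying that the trial's result will be biased, or in which direction. The point should be fixed, but it does not invalidate the design.

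**What to change.** 1. Keep within ±3° of target, with its exact 95% interval, as the primary endpoint.
2. In 10.5, pre-specify the proportion of study knees within 0° ± 3° on the same 1-month long-leg film, with an exact 95% interval compared with 73.4%.
3. State superiority over the reference series in mechanically aligned knees only if the primary criterion is met and this second lower limit also exceeds 73.4%. Both must pass, so the 5% level needs no split. Otherwise, report the target-based result with the statement that 73.4% is not established as a rate around target.
4. In 3.1 and 10.5, say how target is defined for scoring. If it is 0° for every knee, saying so makes the two analyses identical.
5. In 10.1, say which definition the 88% refers to.

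**Cost.** No new data are needed: the target (7.3) and the film (7.4) are already collected. A protocol amendment with IRB/EC approval is needed (11.2). The sample size stays at 120, and the primary test keeps about 97–98% power at 88%. The downside is that knees with targets away from 0° may count as failures in the added analysis. With 88% on target, it passes in about 95%, 72% or 20% of trials at n = 115 for target SD 0.5°, 1.0° or 1.5°. Its power may therefore fall below 80% even if the device is accurate to target, and the protocol should say so.

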1.2. Study Rationale

The purpose of this study is to demonstrate superior accuracy with the Navio[°] Robotic-assisted Surgical System in achieving desired post-operative mechanical alignment, compared to TKA procedures using standard instruments. An additional study purpose is to document clinical and patient-reported outcomes in subjects receiving TKA with the Navio[°] system.

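### The stated aim is superiority to TKA with standard instruments, but the test in 10.5 supports only that Navio exceeds a fixed 73.4% literature benchmark

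*Combined protocol and SAP*

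**What the plan says.** Three places set the aim as a comparison with conventional surgery:
- The synopsis (Study Purpose) seeks superior accuracy "compared to TKA procedures using standard instruments, as well as to document clinical and patient-reported outcomes".
- Section 1.2 repeats it: "compared to TKA procedures using standard instruments".
- The primary objective in 2.1 is superiority in reaching alignment within ±3° of target, "as compared to TKA procedures using standard instruments".

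The statistical sections define something narrower. Section 10.1 takes its benchmark from one published series: "They found that of the 398 TKAs reviewed in the paper there were 292 (73.4"%) with a mechanical axis of 0° ± 3°. It tests "against the reference proportion of 73.4% from above" and calls success "hence proving superiority to the reference literature". Section 10.5 uses an exact binomial interval for the Navio proportion alone, and superiority to the reference literature "will be achieved if the lower limit of the two-sided 95% confidence interval is greater than 73.4"%. The endpoint there is ±3° from target.

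The synopsis and section 4 disclose the historical control. Section 10.2 announces a separate SAP, which is not among the documents.

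**The concern.** The objective and the test answer different questions. If 10.5 is met, the report can properly say that the Navio proportion exceeds 73.4%. Read against 2.1, the same result would be reported as superiority to standard instruments. Two steps lie between those statements, and the plan supports neither.

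First, for a claim about a type of surgery, 73.4% is a sample estimate. The one-sample interval treats it as known. Second, nothing in 10.1 says how the 398 reference knees were operated on, and the reference counts alignment around 0° while this study counts it around a target recorded at surgery (7.3). At stake is the wording of the main conclusion, since the plan provides no other comparison with conventional TKA.

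**Working it through.** **Inputs.** Reference 292/398, benchmark 0.734, assumed Navio rate 0.88, 115 evaluable, 120 recruited (10.1); two-sided 5%, so 2.5% for the lower limit (10.2); exact one-sample interval (10.5). Section 10.1 expects that "approximately 5% of subjects will be lost to follow up at the 1 month visit", and 120 × 0.95 = 114, so 114, 115 and 120 are all shown.

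**1. The plan's own figures.** 292/398 = 0.7337, which agrees with 73.4%. The exact lower limit for x successes in n is the 0.025 quantile of Beta(x, n − x + 1). The smallest x with a limit above 0.734, and P(X ≥ x), are:

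| n | Cut-off | Lower limit at cut-off | Error at true 73.4% | Power at true 88% |
|---|---|---|---|---|
| 114 | 94 | 74.2% | 1.58% | 97.0% |
| 115 | 94 | 73.45% | 2.43% | 98.2% |
| 120 | 98 | 73.6% | 2.27% | 98.5% |

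Against a fixed 73.4% the rule keeps its level. The stated 80% power at 115 is not reproduced (98.2% under this rule); that is a separate matter and does not weaken the test.

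**2. Uncertainty of the benchmark.** With independent knees, the exact 95% CI for 292/398 is 68.7% to 77.6%. Its standard error is √(0.7337 × 0.2663/398) = 2.2 points, against √(0.734 × 0.266/115) = 4.1 points for the Navio proportion. The rule counts only the second.

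**3. Error for the broader claim.** Let both true rates be 0.734 and let the reference count Y be Binomial(398, 0.734). False superiority is the sum over y of P(Y = y) × P(lower limit for X/n exceeds y/398). This gives 3.29% (n=114), 3.33% (n=115) and 3.40% (n=120), against 2.5%.

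Given the 292/398 actually seen, the error depends on the unknown true standard rate. At n=115 it is 0.3% if that rate is 70%, 2.4% at 73.4%, 5.6% at 75% and 17% at 77.6%.

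**4. Effect on the decision.** Compare the Navio count with 292/398 by the Newcombe interval, lower limit = d − √[(p₁ − l₁)² + (u₂ − p₂)²], where l₁ and u₂ are Wilson limits. For 94/115:
- p₁ = 0.8174, l₁ = 0.7369; p₂ = 0.7337, u₂ = 0.7747; d = 0.0837
- lower limit = 0.0837 − √(0.0805² + 0.0411²) = 0.0837 − 0.0903 = −0.0066

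So 94/115 meets 10.5 although the two-sample interval includes zero. At 95/115 the lower limit is +0.0030. Cut-offs by method:

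| n | Rule in 10.5 | Newcombe or Miettinen-Nurminen, independent knees | Fisher | Newcombe, assumed design effect 2 (reference size 199) |
|---|---|---|---|---|
| 114 | 94 | 94 | 94 | 95 |
| 115 | 94 | 95 | 95 | 96 |
| 120 | 98 | 99 | 100 | 100 |

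At n=115 the rule and the Newcombe interval disagree only at exactly 94 successes, which has probability 1.5% if the true rate is 88%.

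**The case against.** The strongest reply is that the plan is open about what it does. The historical control is disclosed, 10.1 gives the source and counts of the benchmark, and 10.1 and 10.5 word success as superiority to the reference literature. A fixed literature benchmark is a common choice in a single-arm study. The 3.3% averages over redraws of a reference sample that has already been observed, and at n=114, the size the plan itself expects, the two-sample cut-off equals the plan's. The absent SAP might also contain a supportive comparison.

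Most of this stands, and it is why the point is minor. It does not align 2.1 with 10.5: disclosing a design does not change what the objective claims, and an SAP that added an interval would leave the objective's wording as it is. The lack of a supportive interval can be asserted only for 10.5.

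A reader might infer three stronger things that the documents do not support:
- *That the test in 10.5 is invalid.* It holds its level against the value it names.
- *That false superiority is 17%.* That needs a true standard rate at the upper end of the reference's interval; at 70% the error is 0.3%.
- *That a two-sample interval above zero would justify the claim about standard instruments.* It repairs only the sampling error. Section 10.1 does not identify the reference technique, and the alignment definitions differ.

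**Conclusion.** The point holds as a mismatch between objective and test. The rule in 10.5 supports exceeding the 73.4% literature benchmark. It does not support superiority to TKA with standard instruments at the stated error level: about 3.3% to 3.4% against 2.5% on sampling error alone, assuming 398 independent reference knees and a shared true rate of 73.4%. The documents count knees and give no patient number, so independence cannot be checked; the design effect of 2 is an assumed upper bound.

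The cut-off moves by none or one subject with a Newcombe or Miettinen-Nurminen interval and independent knees. It can move by two with Fisher's test (at n=120) or under the assumed design effect of 2 (at n=115 and 120). The unquantified differences in instruments, population, era and alignment definition limit the broader claim too, and no interval against 292/398 addresses them. Severity: minor.

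**What to change.** 1. Keep the success rule in 10.5 as it is.
2. In the synopsis, 1.2, 2.1 and the report, limit the conclusion to exceeding the 73.4% literature benchmark.
3. Add to 10.5, as a pre-specified supportive analysis, the Newcombe or Miettinen-Nurminen 95% CI for the Navio proportion minus 292/398.
4. State beside it that the interval assumes independent reference knees and does not address differences in instruments, population, era or alignment definition. It should not be used to reinstate the claim about standard instruments.

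The cost is a protocol wording amendment and one extra analysis. Under 11.2 the amendment needs agreement between sponsor and investigator, and IRB/EC approval where it may affect scientific soundness. No subjects or data are added, and power is unchanged because the success rule is unchanged.
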